7.1 Sample Size Determination

This is a proof-of-concept study and therefore a power calculation was not performed. The primary endpoint of this study is the safety of this drug in terms of incidence of rate of treatment emergent major infection, grade 3 or 4 anemia, leukopenia or thrombocytopenia in patients with PGNMID and C3 GN associated with monoclonal gammopathy and the secondary endpoint is to the efficacy of daratumumab in this patient population. A paired t-test will be utilized to test the hypotheses described below. Twelve subjects will be enrolled in the study.

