3.3 Secondary Endpoints

Proportion of patients achieving complete or partial remission where the responses are defined as below:

- a) Complete Response at 12 months
 - < 300 mg proteinuria/24 hours
 - No greater than a 15% reduction in GFR as determined by creatinine clearance
- b) Partial Response at 12 months
 - > 50% reduction in 24 hour proteinuria
 - No greater than a 30% reduction in baseline GFR as determined by creatinine clearance
- c) No Response at 12 months
 - \leq 50% reduction, unchanged or increasing proteinuria over baseline levels

- A greater than a 30% reduction in baseline GFR as determined by creatinine clearance
- d) Improvement in hematuria (Categorical: <3 rbc/hpf; 3-10 rbc/hpf; 10 to 50; 50 to 100; >100 rbc/hpf)
- e) Improvement in complement 3 level (increase of 25% from baseline)

4 Subject Selection Enrollment and Withdrawal

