7.2 Statistical Methods

Descriptive Statistics

Univariate descriptive statistics and frequency distributions will be calculated, as appropriate for all variables. Baseline values for demographic, clinical, and outcome variables (primary and secondary) in each response category will be tabulated. Time-to-response will be analyzed descriptively with Kaplan-Meier method.

For the primary endpoint, the number and proportion of patients with treatment-emergent major infections, grade 3 or 4 anemia, leukopenia or thrombocytopenia will be summarized. Changes in Hgb, WBC count and platelet count from baseline (Day 0) will be analyzed through a paired t-test by comparing post-baseline to baseline values. The secondary endpoint of the proportion of patients with complete or partial response will be summarized in a similar manner.

It is expected that 9 patients will enter the OLE. The rate of relapse in addition to the time to relapse from the last dose of daratumumab to initiation of retreatment will be evaluated. Paired t-test will be used to evaluate change in the proteinuria from time of relapse to the end of the study. Rate of CR and PR will be evaluated at the end of the OLE.

Handling of Missing Data

This is a study of only 12 patients and expect that majority of patients will have complete data available.

Primary Hypothesis: Daratumumab is safe and well-tolerated in patients with PGNMID and C3GN associated with monoclonal gammopathy

To test this hypothesis, the incidence of major infection will be examined, specifically the development of pneumonia, severe urinary tract infection/pyelonephritis, sepsis, meningitis will be reported. In addition, anemia, leukopenia, thrombocytopenia will be examined by evaluating changes in Hgb, WBC count and platelet count, respectively. Statistical significance will be assessed using paired t-test comparing 6 months and 1 year value compared to baseline. The

number of patients who had to discontinue drug due to side effect (drop in blood counts, infection) will also be reported.

Secondary Hypothesis: Daratumumab is effective in inducing remission (defined as improvement in proteinuria and eGFR) in patients with PGNMID and C3GN associated with monoclonal gammopathy

A paired t-test will be performed to assess change in proteinuria and renal function at 6 months and 12 months compared to baseline (screening visit).

Interim Analysis

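### Remission has two meanings in the plan: section 3.3 sets per-patient thresholds, but section 7.2 tests the remission hypothesis only as mean change and gives the CR/PR proportion no interval

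*Combined protocol and SAP*

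**What the plan says.** Section 3.3 makes the secondary endpoint "Proportion of patients achieving complete or partial remission where the responses are defined as below". Both categories are judged per patient at 12 months:

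- CR: proteinuria below 300 mg/24 h and a GFR loss of no more than 15%.
- PR: a fall in proteinuria of more than 50% and a GFR loss of no more than 30%.

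GFR is taken from creatinine clearance and need not improve in either category.

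Section 7.2 (Statistical Methods) words the secondary hypothesis as "Daratumumab is effective in inducing remission (defined as improvement in proteinuria and eGFR"). The analysis placed under it is "A paired t-test will be performed to assess change in proteinuria and renal function at 6 months and 12 months", against the screening value. Section 7.1 announces the same approach for all hypotheses: "A paired t-test will be utilized to test the hypotheses described below".

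For the endpoint itself, section 7.2 says "The secondary endpoint of the proportion of patients with complete or partial response will be summarized in a similar manner". The manner referred to is a number and a proportion. Time to response is descriptive, and no test is named for the CR and PR rate at the end of the extension. No confidence interval, reference rate or success criterion for the CR/PR proportion appears anywhere. The secondary objective in section 2 uses a third wording: complete or partial remission, measured through change in proteinuria and serum creatinine.

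**The concern.** The endpoint counts patients who cross a threshold. The test asks whether an average differs from zero. These are different quantities, and either can be favourable while the other is not. A modest fall shared by everyone yields a small p-value with nobody in remission. A large fall in half the patients can yield an unremarkable p-value.

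This is the trial's only efficacy hypothesis, and it is worded as remission. If the report takes its support from the t-test, the wording will claim more than the test shows. The figure that readers will look for, the share of 12 patients in CR or PR, would appear without any statement of its precision.

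**Working it through.** **Inputs from the documents.** n = 12, single arm ("Twelve subjects will be enrolled in the study"). Baseline proteinuria is at least 1000 mg/24 h (section 4.1), so CR needs a fall of more than 70%. The response thresholds are those of section 3.3. No power, effect size, SD, alpha or sidedness is stated, so there is no planned figure to reproduce. **Assumption:** two-sided 0.05.

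**Step 1: when the test is significant.** The paired t statistic is mean change / (SD of change / √12). The critical value on 11 df is 2.201. Significance needs |mean|/SD > 2.201/√12 = 0.635. The response thresholds play no part in this.

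**Step 2: significant, with no responder (constructed data).**

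- Baselines (mg/24 h): 1200, 1500, 1800, 2200, 2600, 3000, 3500, 4000, 4800, 5500, 6500, 8000.
- Falls (%), in the same order: 30, 20, 40, 25, 35, 45, 15, 30, 40, 20, 35, 25 (mean 30).
- The largest fall is 45% and the lowest final value is 840 mg, so nobody meets the CR or PR proteinuria criterion, whatever happens to GFR: 0/12.
- The mean fall is 13,210/12 = 1101 mg and the SD is 670, so t = 1101/(670/3.464) = 5.69 and p = 0.00014. On the log scale p = 1.4 × 10⁻⁶.
- The result does not hinge on the pairing. Re-pairing the same falls and baselines at random 20,000 times gave a median p of 0.0003 and a largest p of 0.002.
- Renal function can move the same way. GFR changes of 2, 3, 1, 4, 5, 2, 0, 3, 6, -1, 2 and 4 have mean 31/12 = 2.58 and SD 2.02, so t = 4.43 and p = 0.001. Both parts of the section 7.2 wording are then met with 0/12 in remission under section 3.3.

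**Step 3: how easily this arises.** Simulation of 12 patients, 20,000 runs per setting. The assumptions are a log-normal baseline with median 3000 mg, log-SD 0.6 and a floor of 1000 mg, and log-normal change.

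| True median fall | Log-SD of change | Trials with p < 0.05 | Of those, no patient meeting a proteinuria criterion |
|---|---|---|---|
| 20% | 0.15 | 96% | 99% |
| 20% | 0.20 | 81% | 89% |
| 20% | 0.25 | 62% | 68% |
| 30% | 0.15 | 99.8% | 86% |
| 30% | 0.25 | 94% | 32% |

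**Step 4: the converse.** Same baselines, with final/baseline ratios of 0.2, 0.2, 0.3, 0.3, 0.3, 0.4, 1.1, 1.1, 1.2, 1.2, 1.3 and 1.1, and GFR assumed stable. Six patients fall by 60-80% and are responders; six rise by 10-30%. The mean fall is 252 mg and the SD 1313, so t = 252/(1313/3.464) = 0.66 and p = 0.52. Another set of this kind gave p = 0.27. The listed set is unfavourable, because its responders have the lowest baselines: under random re-pairing the median p was 0.11, and about 6% of pairings reached p < 0.05 in favour. On the log scale the same ratios give p = 0.028 under any pairing. The converse is therefore a raw-scale result, and the plan does not state a scale.

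**Step 5: the missing interval.** Clopper-Pearson limits for k of 12 are the 2.5% quantile of Beta(k, 13 - k) and the 97.5% quantile of Beta(k + 1, 12 - k). For k = 0 the upper limit is 1 - 0.025^(1/12) = 26.5%.

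| CR+PR | Exact 95% CI |
|---|---|
| 0/12 | 0-26.5% |
| 3/12 | 5.5-57.2% |
| 6/12 | 21.1-78.9% |
| 9/12 | 42.8-94.5% |

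**The case against.** The best defence is that the plan says what it means by remission at that point. Section 7.2 explains it as improvement in proteinuria and eGFR, and the objective in section 2 speaks of change in proteinuria and serum creatinine. On that wording a t-test of change is the matching test. This stands as an account of how the mismatch arose. It does not remove it, because section 3.3 defines CR and PR by thresholds and does not require GFR to improve. The document then holds two meanings of one word, and the endpoint uses the one that is not tested.

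A second defence is scale: "This is a proof-of-concept study and therefore a power calculation was not performed", the primary objective is safety, and describing a proportion in 12 patients is acceptable in itself. That stands too, and it limits the severity.

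Two stronger readings are tempting, and the documents support neither:

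- **That the plan would declare efficacy on p < 0.05 with no remissions.** No alpha and no efficacy success rule is stated, and the CR/PR count would be reported beside the t-tests, so 0/12 would be visible. The risk is a conclusion worded beyond its test, not a concealed result.
- **That the t-test passes off lost filtration as benefit.** A patient whose proteinuria falls by more than half with a GFR loss above 30% cannot be CR or PR, and the proteinuria test does count that fall. But renal function is tested separately and the hypothesis names both. Whether such a patient is formally No Response depends on how the two unconnected bullets of section 3.3(c) are read.

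**Conclusion.** The concern holds in this form: remission carries two conflicting meanings, the tested one is not the endpoint, and the endpoint has no interval. A statement about inducing remission does not follow from a paired t-test of mean change. Such a test can give p of 0.0001 to 0.0003 with 0/12 in CR or PR, and can be non-significant on the raw scale with 6/12 responding.

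That the two quantities can diverge follows from the definitions. The p-values and simulated frequencies rest on the assumed two-sided 0.05 level, the constructed data and the assumed spreads. The exact limits need only n = 12.

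Severity is moderate: it should be fixed, but it does not undermine the trial. A reader might also infer that the plan needs an untreated remission rate for the lower limit to exceed. The documents give no such rate, and the point does not depend on one.

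**What to change.** In section 7.2 (Statistical Methods):

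1. Replace the explanation of remission inside the secondary hypothesis with a reference to the CR and PR definitions of section 3.3, and bring the objective in section 2 into line.
2. Base any statement about remission on the proportion in CR or PR at 12 months in the all-treated population, with an exact (Clopper-Pearson) 95% CI. Report CR alone in the same way.
3. Label the t-tests of proteinuria and renal function as supportive evidence of mean change only, and amend the general sentence in section 7.1 to match.

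The cost is wording alone: no added patients, visits or assays. The price is candour about precision. Even 9/12 responders would carry an interval of 42.8-94.5%, so the efficacy claim becomes more modest.

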7.2 Statistical Methods

Descriptive Statistics

Univariate descriptive statistics and frequency distributions will be calculated, as appropriate for all variables. Baseline values for demographic, clinical, and outcome variables (primary and secondary) in each response category will be tabulated. Time-to-response will be analyzed descriptively with Kaplan-Meier method.

For the primary endpoint, the number and proportion of patients with treatment-emergent major infections, grade 3 or 4 anemia, leukopenia or thrombocytopenia will be summarized. Changes in Hgb, WBC count and platelet count from baseline (Day 0) will be analyzed through a paired t-test by comparing post-baseline to baseline values. The secondary endpoint of the proportion of patients with complete or partial response will be summarized in a similar manner.

It is expected that 9 patients will enter the OLE. The rate of relapse in addition to the time to relapse from the last dose of daratumumab to initiation of retreatment will be evaluated. Paired t-test will be used to evaluate change in the proteinuria from time of relapse to the end of the study. Rate of CR and PR will be evaluated at the end of the OLE.

Handling of Missing Data

This is a study of only 12 patients and expect that majority of patients will have complete data available.

Primary Hypothesis: Daratumumab is safe and well-tolerated in patients with PGNMID and C3GN associated with monoclonal gammopathy

To test this hypothesis, the incidence of major infection will be examined, specifically the development of pneumonia, severe urinary tract infection/pyelonephritis, sepsis, meningitis will be reported. In addition, anemia, leukopenia, thrombocytopenia will be examined by evaluating changes in Hgb, WBC count and platelet count, respectively. Statistical significance will be assessed using paired t-test comparing 6 months and 1 year value compared to baseline. The

number of patients who had to discontinue drug due to side effect (drop in blood counts, infection) will also be reported.

Secondary Hypothesis: Daratumumab is effective in inducing remission (defined as improvement in proteinuria and eGFR) in patients with PGNMID and C3GN associated with monoclonal gammopathy

A paired t-test will be performed to assess change in proteinuria and renal function at 6 months and 12 months compared to baseline (screening visit).

Interim Analysis

Interim analysis will be done every 6 months to assess safety of the drug. The study will be stopped if four patients experience serious adverse events including infection, anemia, thrombocytopenia or leucopenia resulting in discontinuation of study drug.

A four person Data Safety Monitoring Board (DSMB) comprised of clinical researchers not affiliated with the study will be established and responsible for evaluating the ongoing progress of the study. The DSMB will communicate by meeting every 6 months to review interim analysis. The Chairperson of the DSMB will be notified of SAEs within 48 hours of them being reported and the Chair will have an additional 48 hours in which to respond and determine whether an emergency of the DSMB is required. The DSMB will act in an advisory capacity to the PI's to monitor participant safety, data quality and evaluate the progress of the study.

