3.1 General Design

This study is an open-label phase 2 trial of the safety and efficacy of daratumumab, in the treatment of PGNMID and C3GN associated with monoclonal gammopathy. Subjects will be screened at outpatient Nephrology Clinic visit appointments and interested qualified subjects will be consented and offered participation in this trial. Once consent has been obtained baseline values will be established and subjects will begin treatment and follow-up for the next 12 months. Daratumumab will be administered once weekly for 8 weeks and then once every 2 weeks for 8 additional doses. Patients will be followed for a total of 12 months (6 months after the last infusion). A final visit for evaluation and collection of lab samples will be conducted at the end of the study.

3.2 *The clinical course of the patients who have achieved complete or partial remission following daratumumab is unclear, therefore these patients who have consented to the OLE and achieved complete or partial remission, will be followed for 24 months following completion of the main trial. In the OLE, patients will be assessed every 3 to 6 months. Relapse is defined as a 30% increase in proteinuria from the lowest level the patient has achieved and will be documented with two 24 hour urine collections two weeks apart. If there is evidence of relapse, patients will receive 12 additional doses of daratumumab(16 mg/kg). The first 8 doses will be given weekly and the last 4 doses will be administered every other week. Primary Endpoints*

Incidence of major infection (defined as the development of pneumonia, severe urinary tract infection/pyelonephritis, sepsis, meningitis), grade 3 or 4 anemia, leukopenia or thrombocytopenia and changes in HgB, WBC count and platelet count from baseline to 6 month and 12 month timepoints.

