4.4 Early Withdrawal of Subjects

4.4.1 When and How to Withdraw Subjects

- Subjects decision to withdraw from the study (withdrawal of consent)
- Failure of subject to adhere to protocol requirements (missing more than two infusions within the first 8 weeks or more than three infusions in the following 4 months). If a patient experiences an adverse event and the PI determines the next dose must be delayed, the dose may be delayed for up to 4 weeks and continue on the protocol schedule without being withdrawn.
- Disease progression (> 50% increase in proteinuria and > 30% reduction in GFR as measured by creatinine clearance) at day 77 visit
- Severe infection (defined as the development of pneumonia, severe urinary tract infection/pyelonephritis, sepsis, meningitis)
- If Hgb < 8.0 g/dL or platelet < 50,000, or WBC < 3.0 or absolute neutrophil count (ANC) < 500, the infusion will be held and restarted once blood counts have improved.

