5.6 Prior and Concomitant Therapy

The patient should be off of all immunosuppressive therapies (cyclophosphamide, MMF, cyclosporine, tacrolimus, azathioprine, ACTH) within three months of enrollment in the study. If patient has received rituximab prior to the study there should be evidence of B-cell reconstitution prior to enrollment (CD 20 count >5). The subject should be off of prednisone or glucocorticoid equivalent in the last 6 weeks prior to enrollment, unless they are being treated with low dose oral prednisone or glucocorticoid for a condition unrelated to PGNMID or C3GN (e.g., asthma, gout) at a daily dose of 10mg or less.

Patients can receive ACE-I or ARB while enrolled in the study but dose adjustment is not allowed unless down titration for safety reasons.

Rescue treatment is not permitted while receiving daratumumab. If patient is failing treatment with evidence of disease progression (> 50% increase in proteinuria and > 30% reduction in GFR based on creatinine clearance) on visit day 77, the subject will be withdrawn from the study and can then receive other immunosuppressive therapy per discretion of the treating physician.

Management of Hepatitis B Virus Reactivation

Primary antiviral prophylaxis is permitted as per local standard of care. Per protocol, HBV DNA testing by PCR is mandatory for subjects at risk for HBV reactivation see Section 6.

For subjects who are diagnosed with HBV reactivation while on treatment, study treatment should be interrupted until the infection is adequately controlled. If the benefits outweigh the risks, study treatment may be resumed with concomitant antiviral prophylaxis as per local standard of care. Consult a liver disease specialist as clinically indicated.

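### Section 7.2 describes time-to-response by Kaplan-Meier with no rule for patients withdrawn before responding, so under default censoring the curve can exceed the all-treated response proportion

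*Combined protocol and SAP*

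**What the plan says.** The only statement on the timing of response is in Section 7.2, Descriptive Statistics: "Time-to-response will be analyzed descriptively with Kaplan-Meier method". No censoring rule or treatment of competing events accompanies it. The missing-data paragraph says only that most of the 12 patients should have complete data.

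Section 4.4.1 lists reasons for withdrawal. Two matter here: "Disease progression (> 50% increase in proteinuria and > 30% reduction in GFR as measured by creatinine clearance) at day 77 visit", and "Severe infection (defined as the development of pneumonia, severe urinary tract infection/pyelonephritis, sepsis, meningitis"). For progression, Section 5.6 adds that "the subject will be withdrawn from the study and can then receive other immunosuppressive therapy per discretion of the treating physician". Section 4.4.2 sends patients withdrawn for safety or non-adherence to clinical follow-up or back to the referring nephrologist, with no scheduled response assessment. Section 5.5 does promise continued research follow-up, but in its paragraph on missed infusions and for safety.

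Section 3.3 defines complete, partial and no response at 12 months only. Section 7.2 separately reports the number and proportion with complete or partial response. The one defined analysis population is all patients who received at least one dose.

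**The concern.** Kaplan-Meier treats a censored patient as having the same later chance of response as those still under observation. A patient withdrawn at Day 77 with a large rise in proteinuria and a large loss of GFR is close to the opposite of a responder, and may then start other immunosuppression. Censoring that patient passes his or her weight to the patients who remain. Patients withdrawn for severe infection also leave scheduled response assessment, so by default they too are censored at exit.

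One minus Kaplan-Meier (1 − KM) then answers a hypothetical question: how many would respond if nobody were withdrawn? In an uncontrolled study of 12 patients, readers are likely to take it as the share who responded. It could stand beside a lower complete/partial response proportion for the same patients, and the gap would come from those who failed or were harmed.

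**Working it through.** The plan gives no response rate or time-to-response figure to reproduce ("a power calculation was not performed"), so the check uses scenarios.

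**Inputs from the documents**
- Sample size: "Twelve subjects will be enrolled in the study" (Section 7.1).
- Expected extension entry: "It is expected that 9 patients will enter the OLE" (Section 7.2).
- Extension condition: "these patients who have consented to the OLE and achieved complete or partial remission, will be followed for 24 months" (extension paragraph after Section 3.1). Nine entrants therefore imply at least nine responders.

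**Assumptions**
- Exactly R = 9 of 12 respond.
- w of the 3 non-responders are withdrawn before the responses and censored at exit.
- The other non-responders are followed to Day 365, with no other censoring.

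**Formulas**
- 1 − KM = 1 − ∏(1 − d/n). If all w withdrawals precede the first response, the risk set starts at 12 − w and the product telescopes to 1 − KM = R/(12 − w).
- Cumulative incidence with withdrawal as a competing event = R/12.
- Standard error of the proportion = √(0.75 × 0.25/12) = 12.5 points.

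| w | 1 − KM | Cumulative incidence | Difference |
|---|---|---|---|
| 0 | 9/12 = 75.0% | 75.0% | 0 |
| 1 | 9/11 = 81.8% | 75.0% | 6.8 points (0.55 SE) |
| 2 | 9/10 = 90.0% | 75.0% | 15 points (1.2 SE) |
| 3 | 9/9 = 100% | 75.0% | 25 points (2.0 SE) |

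**Sensitivity to timing**
- Assume 2, 3, 2 and 2 responses at Days 77, 161, 264 and 365, with withdrawals at Day 77 just after that visit's responses.
  - w = 1: 1 − (10/12)(6/9)(4/6)(2/4) = 81.5%.
  - w = 2: 1 − (10/12)(5/8)(3/5)(1/3) = 89.6%.
  - w = 3: the last factor is 0/2, so 100%.
- All responses by Day 161 (4 at Day 77, 5 at Day 161) and three withdrawals at Day 200: 1 − (8/12)(3/8) = 75.0%, so no difference.
- Response countable only at 12 months, as Section 3.3 is written: every earlier withdrawal precedes response, and three give 9/9 = 100%.

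**Sensitivity to response rate.** If 6 of 12 respond, 1, 2 or 3 earlier withdrawals give 6/11 = 54.5%, 6/10 = 60.0% or 6/9 = 66.7%, against 50.0%.

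**The case against.** The plan does not say that withdrawn patients are censored at exit. Kaplan-Meier with such patients kept at risk to Day 365 would not have the problem, so the defect is an unstated rule combined with an unsuitable default. That stands, and the point is worded accordingly.

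Little rests on the curve. It is descriptive, time-to-response is not among the endpoints in Section 3.3, and no test or stopping rule uses it. How often patients respond is reported separately. This also stands, and limits the importance of the point.

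Four stronger readings are tempting, but the documents do not support them.
- *The curve will read 100%.* That is a ceiling. It requires all three non-responders to leave no later than the last response visit, and nine is expected extension entry, not a stated response rate.
- *Severe infection ends any chance of response.* Response is judged about six months after the last infusion, so a patient withdrawn for infection after several doses might still respond. Treating this exit as a competing event is a choice of estimand. Death, for its part, is not listed in Sections 4.4.1 or 5.6.
- *The number of withdrawals can be predicted.* Section 1.4 gives pneumonia as 11%, which would mean 12 × 0.11 = 1.3 cases and a 1 − 0.89¹² = 75% chance of at least one. But the earlier trials described were in myeloma, this protocol gives antimicrobial prophylaxis, and a case need not precede response. The documents give no frequency for Day 77 progression.
- *Kaplan-Meier is biased by about 7 points on average.* Assume 75% would respond, equally often at Days 77, 161, 264 and 365, and 11% are withdrawn independently of response, uniformly over Days 1 to 162. Cumulative incidence is then 0.75 × (0.948 + 0.891 + 0.890 + 0.890)/4 = 67.8%, while 1 − KM recovers 75.0%. That 7-point gap separates two different questions. It does not show informative censoring.

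**Conclusion.** The point holds as a gap that should be closed. Section 7.2 names Kaplan-Meier, gives no rule for withdrawal before response, and sits beside withdrawal rules of which at least one, Day 77 progression, is clearly related to response. Under default censoring the curve can exceed the all-treated proportion by 0 to 25 points when 9 of 12 respond: about 7 points for one early withdrawal and 15 for two. These figures rest on the assumed nine responders, on censoring at exit, and on withdrawals that precede the responses. The complete/partial response proportion is unaffected if all treated patients form its denominator. A related gap is that Section 3.3 defines response only at 12 months, so no date of response exists for any time-to-response method.

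**What to change.** Replace the sentence in Section 7.2 with wording such as: *Time to response will be described in the all-treated population by the cumulative incidence function (Aalen-Johansen). Withdrawal for progression or severe infection, start of other immunosuppression, and death, when they occur before response, are competing events. Only patients with otherwise incomplete follow-up are censored. The response date is the first scheduled visit with 24-hour urine protein and creatinine clearance at which the Section 3.3 thresholds for complete or partial response are met.*

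A simpler alternative is to keep patients with a competing event in the risk set as non-responders to Day 365. With no other censoring before then, it gives the same R/12.

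The cost is a few lines of text and a standard procedure, with no extra data. If nobody is withdrawn before responding and no competing event occurs, the curve is the same as Kaplan-Meier. Otherwise it is lower, and it describes response under the treatment policy including withdrawals, not a hypothetical response without them. The plan should say that this is the quantity intended.

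### OLE time to relapse ends at retreatment, so no first event is possible for nominally 203 days after the last dose; the paired t-test from relapse starts from a value selected for being high

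*Combined protocol and SAP*

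**What the plan says.** All references are to the combined protocol and SAP.

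- **Time to relapse (Section 7.2).** The plan states that "time to relapse from the last dose of daratumumab to initiation of retreatment will be evaluated". It names no estimation method or censoring rule for this endpoint; Kaplan-Meier is mentioned only for time to response.
- **Change after relapse (Section 7.2).** "Paired t-test will be used to evaluate change in the proteinuria from time of relapse to the end of the study". No comparator, alpha or sidedness is given for this test.
- **Other OLE summaries (Section 7.2).** "Rate of CR and PR will be evaluated at the end of the OLE", and on numbers, "It is expected that 9 patients will enter the OLE".
- **Relapse (Section 3, the OLE paragraph numbered 3.2).** The relapse rule reads: "30% increase in proteinuria from the lowest level the patient has achieved and will be documented with two 24 hour urine collections two weeks apart".
- **OLE population and timing (same paragraph).** The OLE covers "these patients who have consented to the OLE and achieved complete or partial remission". On duration, OLE participants "will be followed for 24 months following completion of the main trial". Visits are every 3 to 6 months.
- **Retreatment (Study Summary and Section 5.2).** Further daratumumab is given to OLE patients who relapse, with at most 3 courses in 24 months. No retreatment is provided for in the main study.
- **Dates (Section 4.3).** The 16th infusion is on Day 162 and the final main-study visit on Day 365.

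**The concern.** Section 3 gives the reason for the OLE: the course of patients after remission on daratumumab is not known. Time to relapse is the analysis that speaks most directly to this. As defined, it measures when retreatment started, not when proteinuria rose, and the design rules out retreatment for more than six months after the last dose. A reader who takes the result as durability off drug would be reading an interval with a built-in minimum.

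The t-test raises a different problem. A patient enters it only after two high readings relative to the lowest value on record. Later readings then tend to be lower whether or not retreatment works, and no control group shows how much of the fall to expect. The plan also does not say which of up to 3 relapses, or which of the two qualifying collections, supplies the starting value.

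**Working it through.** **Inputs from the documents.** Last dose Day 162; final visit Day 365; follow-up visits at Day 264 and Day 365; two collections two weeks apart; threshold 1.3 times the lowest value. The plan gives no power, precision or event figure for the OLE to reproduce.

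**1. Dosing calendar.** Eight weekly doses from Day 1 end on Day 1 + 7×7 = Day 50. Eight more at 14-day intervals end on Day 50 + 8×14 = Day 162, which matches Section 4.3.

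**2. Interval with no possible first event.** 365 − 162 = 203 days (203/30.44 = 6.7 months). If the Day 365 collection is the first of the qualifying pair, the earliest event is 203 + 14 = 217 days. The 203 days are nominal:
- last dose 4 weeks late (Day 190; Section 4.4.1 allows the delay) and Day 365 unchanged: 365 − 190 = 175;
- last two infusions missed (last dose Day 134): 365 − 134 = 231;
- last three missed (last dose Day 120): 365 − 120 = 245. Section 4.4.1 tolerates three misses in this period; Section 5.5 tolerates two.

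**3. Late dating.** Within the OLE, retreatment follows the confirming collection, so the recorded date is at least 14 days after first detection. For a rise first seen at Day 264 in a patient still in complete or partial remission (CR/PR), it is at least 365 − 264 = 101 days late.

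**4. Effect on the median: illustration only.** Assume a Weibull time from last dose to relapse with a median of 365 days. Let F be its distribution function, S = 1 − F, and let a fraction f of relapsers before day 203 never enter the OLE while the rest are counted at about day 203. The observed median t solves S(t) = 0.5 × [1 − f × F(203)].

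| Shape | F(203) | Overstatement, f = 0 | f = 0.5 | f = 1 |
|---|---|---|---|---|
| 0.7 | 0.369 | 0 | 162 days | 390 days |
| 1 | 0.320 | 0 | 92 days | 203 days |
| 2 | 0.193 | 0 | 26 days | 53 days |
| 3 | 0.112 | 0 | 10 days | 20 days |

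Example, shape 1 and f = 1: S(t) = 0.5 × 0.680 = 0.340; t = 365 × ln(1/0.340)/ln 2 = 568; 568 − 365 = 203. If every early relapser enters and is retreated promptly, the median is not shifted at all.

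**5. Selection in the t-test: direction.** If X is a patient's reading and c the threshold, the mean of X given X > c exceeds the mean of X. A second collection does not undo this, because both must pass the same threshold, and the reference is itself a minimum and so tends to lie below the true level.

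**6. Selection in the t-test: illustration of size.** Assume a constant true level, log-normal noise with log-SD 0.10 to 0.30, 9 entrants, 4 or 8 OLE visits, one or four earlier values feeding the minimum, the first qualifying value as start and one end value. Only relapsers are tested, two-sided 0.05 on the mg scale.
- The geometric mean ratio of end to start is 0.83 to 0.89, a fall of 11 to 17% with no drug effect.
- A significant fall occurs in 0.7 to 26.5% of trials if all patients share one level, and in 0.4 to 14.3% with between-patient log-SD 0.8. The nominal rate in that direction is 2.5%.
- If half of entrants truly relapse (1.5- to 2-fold step, still no drug effect), the figures are 2.9 to 15.5% and 1.6 to 9.7%.

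A second set of assumptions (within-patient CV 15 to 40%, one shared level, four earlier values, exactly 5 or 9 relapsers) gives a fall of about 11 to 14.5% and significant results in 8 to 27% (5 relapsers) or 13 to 49% (9 relapsers). Averaging the two qualifying collections leaves the fall essentially unchanged. The direction is stable; the size is not.

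**The case against.** Section 7.2 states both ends of the interval openly, so it is in effect a retreatment-free interval, and the OLE is by design limited to patients who reached remission. That is fair. It supports reporting the quantity under that name, but it does not make it time to relapse, which is what the plan calls it.

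The OLE paragraph stands under descriptive statistics, with no hypothesis or alpha. This lowers the stakes, but a paired t-test is still specified and will yield a p-value.

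Three stronger readings might be inferred, and the documents do not support them.

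- *Early relapsers vanish and durability is overstated by months.* Section 3 implies, but does not state, that OLE entry is judged on the 12-month response. Under that reading, a patient whose proteinuria reduction has slipped to 50% or less by Day 365 counts as No Response in Section 3.3 and lowers the 12-month response rate. The days in step 4 also need an assumed median, shape and fraction excluded. The 175-day figure needs Day 365 to stay fixed, whereas Section 3.1 describes follow-up as six months after the last infusion.
- *The t-test's error rate is badly inflated.* The documents give no within-patient variation. The 26.5% figure requires all patients to share one proteinuria level, which is unlikely when the OLE mixes complete and partial responders. Several ranges start below 2.5%.
- *The relapse definition is wrong because it can be met within remission.* The overlap is real: against the CR limit of "300 mg proteinuria/24 hours", a lowest value below 300/1.3 = 231 mg allows a relapse that still meets it, and for PR the bound is 0.5/1.3 = 38.5% of baseline. But nowhere does the plan equate relapse with loss of remission, retreating early is a defensible trigger, and CR/PR is reported separately at the end of the OLE. This is not a defect.

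**Conclusion.** The concern holds on two counts, and both are minor.

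1. Time to relapse as defined cannot register a first event until nominally 203 days after the last dose. It dates every relapse at retreatment, at least 14 days after detection, and at least 101 days after it for a rise first seen at Day 264 in a patient still in CR/PR. This rests only on the plan's own dates and on retreatment being confined to the OLE. By how much the median would be overstated is not established; it can be zero.
2. The paired t-test from relapse is biased towards a fall because its starting value is selected for being high and there is no comparator. The direction follows from the relapse rule. The size depends on assumed within-patient variation, and with low variation the false-positive rate may be at or below nominal.

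The planned CR/PR rate at the end of the OLE partly protects the conclusions. The OLE is unpowered, expects about 9 patients and does not touch the primary safety endpoint.

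**What to change.** Change the wording of Section 7.2; leave the relapse definition and the retreatment trigger as they are.

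1. **Time to relapse.** Date relapse at the first of the two qualifying 24-hour collections and keep the last dose as time origin. Treat patients as at risk from OLE entry (delayed entry), or label the result as conditional on OLE entry. Report the interval to retreatment separately as the retreatment-free interval. List any 30% rise over the lowest prior value at Day 264 and Day 365, marked as unconfirmed, so that rises before the OLE are visible beside the conditional estimate.
2. **Change after relapse.** Replace the paired t-test with a descriptive summary by course, without a p-value, stating which collection is the starting value. Base the conclusion about retreatment on the planned end-of-OLE CR/PR rate against the original baseline, shown separately for retreated patients.
3. **Optional.** Flag whether each relapse was still within the patient's CR or PR proteinuria limit.

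The change uses collections already planned and adds no visits or patients. Its cost is a less favourable time to relapse and the loss of one p-value in at most about 9 patients.
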